9.4.2. Adverse Events

Programmer note: All of the tables below are shown:

- By treatment at inclusion: Targeted therapy/Other treatments (somatostatin analogs/chemotherapy /...)/ Total.
- By treatment at inclusion: Everolimus/Sunitinib/chemotherapy/somatostatin analogs/interferon alpha/somatostatin analog/metabolic radiotherapy/total.
- By treatment received at least once during the study: Targeted therapy/Other treatments (somatostatin analogs/chemotherapy/...).
- By treatment received at least once during the study: Everolimus/Sunitinib/chemotherapy /somatostatin analogs/interferon alpha/somatostatin analog/metabolic radiotherapy.

As a result, the summary tables will be duplicated.

Table 14.3.2.1: General Overview of Adverse Events – Safety Analysis Set

		Targeted therapies (N=XX)	•••	Total (N=XX)
At least one adverse event	N	XX (XX.X%)	XX (XX.X%)	XX (XX.X%)
Number of adverse events	N	XX	XX	XX
At least one serious adverse event	N	XX (XX.X%)	XX (XX.X%)	XX (XX.X%)
Number of serious adverse events	N	XX	XX	XX
At least one adverse event suspected to be related to the study treatment	N	XX (XX.X%)	XX (XX.X%)	XX (XX.X%)
Number of adverse events suspected to be related to the study treatment	N	XX	XX	XX
At least one adverse event resulting in death	N	XX (XX.X%)	XX (XX.X%)	XX (XX.X%)
Number of adverse events resulting in death	N	XX	XX	XX
At least one adverse event resulting in permanent discontinuation of treatment	N	XX (XX.X%)	XX (XX.X%)	XX (XX.X%)
Number of adverse events resulting in permanent discontinuation of treatment	N	XX	XX	XX
At least one adverse event leading to change in dosage/temporary discontinuation of treatment	N	XX (XX.X%)	XX (XX.X%)	XX (XX.X%)
Number of adverse events leading to change in dosage/temporary discontinuation of treatment	N	XX	XX	XX
At least one adverse event suspected to be related to the study treatment leading to permanent discontinuation of treatment	N	XX (XX.X%)	XX (XX.X%)	XX (XX.X%)

Table 14.3.2.1: General Overview of Adverse Events – Safety Analysis Set

		Targeted therapies (N=XX)		Total (N=XX)
Number of adverse events suspected to be related to the study treatment leading to permanent discontinuation of treatment	N	XX	XX	XX
At least one adverse event suspected to be related to the study treatment resulting in a change in dosage/temporary discontinuation of treatment	N	XX (XX.X%)	XX (XX.X%)	XX (XX.X%)
Number of adverse events suspected to be related to the study treatment leading to change in dosage/temporary discontinuation of treatment	N	XX	XX	XX
At least one adverse event suspected to be related to the study treatment leading to temporary discontinuation of treatment	N	XX (XX.X%)	XX (XX.X%)	XX (XX.X%)
Number of adverse events suspected to be related to the study treatment leading to temporary discontinuation of treatment	N	XX	XX	XX
At least one serious adverse event suspected to be related to the study treatment leading to permanent discontinuation of treatment	N	XX (XX.X%)	XX (XX.X%)	XX (XX.X%)
Number of serious adverse events suspected to be related to the study treatment leading to permanent discontinuation of treatment	N	XX	XX	XX
At least one serious adverse event suspected to be related to the study treatment leading to change in dosage/temporary discontinuation of treatment	N	XX (XX.X%)	XX (XX.X%)	XX (XX.X%)
Number of serious adverse events suspected to be related to the study treatment leading to change in dosage/temporary discontinuation of treatment	N	XX	XX	XX
At least one serious adverse event suspected to be related to the study treatment leading to temporary discontinuation of treatment	N	XX (XX.X%)	XX (XX.X%)	XX (XX.X%)
Number of serious adverse events suspected to be related to the study treatment leading to temporary discontinuation of treatment	N	XX	XX	XX

Table 14.3.2.2: General Overview of Grade ≥3 Adverse Events – Safety Analysis Set

		Targeted therapies (N=XX)	Other treatments (N=XX	Total (N=XX)
At least one adverse event	N	XX (XX.X%)	XX (XX.X%)	XX (XX.X%)
Number of adverse events	N	XX	XX	XX
At least one serious adverse event	N	XX (XX.X%)	XX (XX.X%)	XX (XX.X%)
Number of serious adverse events	N	XX	XX	XX
At least one adverse event suspected to be related to the study treatment	N	XX (XX.X%)	XX (XX.X%)	XX (XX.X%)
Number of adverse events suspected to be related to the study treatment	N	XX	XX	XX
At least one adverse event resulting in death	N	XX (XX.X%)	XX (XX.X%)	XX (XX.X%)
Number of adverse events resulting in death	N	XX	XX	XX
At least one adverse event leading to permanent discontinuation of treatment	N	XX (XX.X%)	XX (XX.X%)	XX (XX.X%)
Number of adverse events leading to permanent discontinuation of treatment	N	XX	XX	XX
At least one adverse event leading to change in dosage/temporary discontinuation of treatment	N	XX (XX.X%)	XX (XX.X%)	XX (XX.X%)
Number of adverse events leading to change in dosage/temporary discontinuation of treatment	N	XX	XX	XX
At least one adverse event suspected to be related to the study treatment leading to permanent discontinuation of treatment	N	XX (XX.X%)	XX (XX.X%)	XX (XX.X%)
Number of adverse events suspected to be related to the study treatment leading to permanent discontinuation of treatment	N	XX	XX	XX
At least one adverse event suspected to be related to the study treatment leading to change in dosage/temporary discontinuation of treatment	N	XX (XX.X%)	XX (XX.X%)	XX (XX.X%)
Number of adverse events suspected to be related to the study treatment leading to change in dosage/temporary discontinuation of treatment	N	XX	XX	XX
At least one adverse event suspected to be related to the study treatment leading to temporary discontinuation of treatment	N	XX (XX.X%)	XX (XX.X%)	XX (XX.X%)
Number of adverse events suspected to be related to the study treatment leading to temporary discontinuation of treatment	N	XX	XX	XX
At least one serious adverse event suspected to be related to the study treatment leading to permanent discontinuation of treatment	N	XX (XX.X%)	XX (XX.X%)	XX (XX.X%)
Number of serious adverse events suspected to be related to the study treatment leading to permanent discontinuation of treatment	N	XX	XX	XX

Table 14.3.2.2: General Overview of Grade ≥3 Adverse Events – Safety Analysis Set

		Targeted therapies (N=XX)	Other treatments (N=XX	Total (N=XX)
At least one serious adverse event suspected to be related to the study treatment leading to change in dosage/temporary discontinuation of treatment	N	XX (XX.X%)	XX (XX.X%)	XX (XX.X%)
Number of serious adverse events suspected to be related to the study treatment leading to change in dosage/temporary discontinuation of treatment	N	XX	XX	XX
At least one serious adverse event suspected to be related to the study treatment leading to temporary discontinuation of treatment	N	XX (XX.X%)	XX (XX.X%)	XX (XX.X%)
Number of serious adverse events suspected to be related to the study treatment leading to temporary discontinuation of treatment	N	XX	XX	XX
At least one grade 3 adverse event	N	XX (XX.X%)	XX (XX.X%)	XX (XX.X%)
Number of grade 3 adverse events	N	XX	XX	XX
At least one serious grade 3 adverse event	N	XX (XX.X%)	XX (XX.X%)	XX (XX.X%)
Number of serious grade 3 adverse events	N	XX	XX	XX
At least one grade 3 adverse event suspected to be related to the study treatment	N	XX (XX.X%)	XX (XX.X%)	XX (XX.X%)
Number of grade 3 adverse events suspected to be related to the study treatment	N	XX	XX	XX
At least one serious grade 3 adverse event suspected to be related to the study treatment	N	XX (XX.X%)	XX (XX.X%)	XX (XX.X%)
Number of serious grade 3 adverse events suspected to be related to the study treatment	N	XX	XX	XX
At least one grade 4 or higher adverse event	N	XX (XX.X%)	XX (XX.X%)	XX (XX.X%)
Number of grade 4 or greater adverse events	N	XX	XX	XX
At least one grade 4 or greater adverse event suspected to be related to the study treatment	N	XX (XX.X%)	XX (XX.X%)	XX (XX.X%)
Number of grade 4 or greater adverse events suspected to be related to the study treatment	N	XX	XX	XX

Programmer note: All of the tables below are shown:

- By treatment received at least once during the study: Targeted therapy/Other treatments (somatostatin analogs/chemotherapy/etc).
- By treatment received at least once during the study: Everolimus/Sunitinib/chemotherapy /somatostatin analogs/interferon alpha/somatostatin analog/metabolic radiotherapy.

Table 14.3.2.3: Adverse Events by System Organ Class and Preferred Term – Safety Analysis Set

	Targeted therapies (N=XX)		Total (N=XX)
SOC 1	XX (XX.X%)	XX (XX.X%)	XX (XX.X%)
Preferred term 1	XX (XX.X%)	XX (XX.X%)	XX (XX.X%)
Preferred term 2	XX (XX.X%)	XX (XX.X%)	XX (XX.X%)
•••			

Using the same template:

Table 14.3.2.4: Adverse Events Suspected to be Related to the Study Treatment by System Organ Class and Preferred Term – Safety Analysis Set

Table 14.3.2.5: Adverse Events Grade =3 by System Organ Class and Preferred Term – Safety Analysis Set

Table 14.3.2.6: Serious Adverse Events Grade =3 by System Organ Class and Preferred Term – Safety Analysis Set

Table 14.3.2.7: Adverse Events Grade ≥4 by System Organ Class and Preferred Term – Safety Analysis Set

Table 14.3.2.8: Adverse Events Grade =3 Suspected to be Related to the Treatment by System Organ Class and Preferred Term – Safety Analysis Set

Table 14.3.2.9: Serious Adverse Events Grade =3 Suspected to be Related to the Treatment by System Organ Class and Preferred Term – Safety Analysis Set

Table 14.3.2.10: Adverse Events Grade ≥4 Suspected to be Related to the Treatment by System Organ Class and Preferred Term – Safety Analysis Set

Table 14.3.2.11: Serious Adverse Events by System Organ Class and Preferred Term – Safety Analysis Set

Table 14.3.2.12: Non-Serious Adverse Events by System Organ Class and Preferred Term – Safety Analysis Set

Table 14.3.2.13: Adverse Events which Resulted in Temporary Discontinuation of Treatment by System Organ Class and Preferred Term – Safety Analysis Set

Table 14.3.2.14: Adverse Events which Resulted in Permanent Discontinuation of Treatment by System Organ Class and Preferred Term – Safety Analysis Set

Table 14.3.2.15: Adverse Events Resulting in Death of the Patient by System Organ Class and Preferred Term – Safety Analysis Set

9.5. Listings

Listing 16.2.1: Protocol Deviations

Patient Sex Age	Reference set	Deviations
XXXXX XXXXX XX	Yes/No	XXXXXXXXXXX XXXXXXXXXXX

Listing 16.2.2: Patients Excluded from the Analysis Sets

Patient Sex Age	Reference set	Safety analysis set	Reason for exclusion from the analysis sets
XXXXX XXXXX XX	Yes/No	Yes/No	XXXXXXXXXXX XXXXXXXXXXX

Listing 16.2.3: Previous Lines of Treatment

Patient Sex Age	Reference set	Treatment group	Previous lines of treatment
XXXXX XXXXX XX	Yes/No	XXXXXXXXX	Line 1: XXXXXXXXXXXX Line 2: XXXXXXXXXXX Line 3: XXXXXXXXXXX

Listing 16.2.4: Lines of Treatment Received Since Starting the Treatment Documented in the Study

Patient Sex Age Initiation - Incident / Prevalent - Reference set	Group	- Visit - Date of visit - Date of tumour assessment	- Radiological response - Clinical response	- Main treatment - Details - Start date - Initial dosage Combination somatostatin analog - Other combination	- Treatment continued - If no, reason	- Concomitant treatment entered - ongoing?	- New concomitant treatment entered - Somatostatin analog? - Other?	- Start date - End date	New Line?	New treatment	Temp. discontinuation
XXXXX	XXX	xxxx	XX	XXXX	XXX			XXXX			
XXXXX XX		XXXX	XX					XXXX			

Listing 16.2.5: Main Treatment Lines Documented in the Study

Patient Sex Age Start Incident / Prevalent Reference		No. of main treatment line No. of main concomitant	Main	Combinat ion with	Initiat ion		
set	Period	treatment line	treatment	the line	date	Stop date	Reason for discontinuation
xxxxx	XXX	XXXX	XXXX	XXXX	XXXX	XXXX	XXXX
XXXXX							
XX							

Listing 16.2.6: Adverse Events

Patient Sex Age	- Safety analysis set - Reference set	- Start date of study treatment - End date of study treatment	adverse	- SOC - PT - Verbatim statement		Outcome [2]	Intensity [3]	CTCAE Grade [4]	Causality	Action on study treatment [5]	Prospective AE (Yes/No)	-Treatments received when the AE developed - Treatments deemed to be received at the time the AE developed (limit 28 days post- discontinuation date)
XXXXX	Yes/No		Yes/no						Not related			,
XXXXX	Yes/No								to			
XX									treatment/			
									Related to			
									treatment			
									XXXX			

^[1] Serious, non-serious.

Using the same template:

Listing 16.2.7: Adverse Events Reported in Patients Excluded from the Safety Analysis Set

Listing 16.2.8: Adverse Events, Grade ≥3

Listing 16.2.9: Serious Adverse Events

Listing 16.2.10: Adverse Events Suspected to be Related to the Study Treatment Leading to Permanent Discontinuation of Treatment

LISTING 16.2.11: Adverse Events Suspected to be Related to the Study Treatment Leading to Temporary Discontinuation of Treatment

^[2] Recovered, recovered with complications, currently recovering, subject not recovered, unknown.

^[3] Mild, moderate, severe.

^{[4] 0, 1, 2, 3, 4, 5.}

^[5] Temporary discontinuation, permanent discontinuation, increase of dosage, reduction of dosage, continued unchanged, unknown, not applicable.

Listing 16.2.12: Deaths

Patient Sex Age	- Safety analysis set - Reference set	Date of death	Reason for death	Details if Other
XXXXX	Yes/No	DDMMYYYY	Related to the	XXXXXXXXXXXXXXXXX
XXXXX	Yes/No		disease/Related to treatment	
XX			/Other	

10. APPENDICES

10.1. Appendix 1: List of Main Chemotherapy Protocols

- ✓ LV5FU2-streptozotocin
- ✓ 5 FU- streptozotocin
- ✓ Interferon alpha-2
- ✓ Adriamycin-streptozotocin
- ✓ Dacarbazine
- ✓ Temozolomide
- ✓ Temozolomide-capecitabine (TEM-CAP)
- ✓ LV5FU2-dacarbazine
- ✓ FOLFIRI = irinotecan + simplified LV5FU2
- ✓ Simplified FOLFOX 4 (or modified FOLFOX 6) = oxaliplatin (EloxatineR) + (EloxatineR) + simplified LV5FU2
- ✓ Simplified LV5FU2
- ✓ XELOX
- ✓ GEMOX = gemcitabine + oxaliplatin
- ✓ CDDP-etoposide
- ✓ Carboplatin-etoposide
- ✓ Irinotecan-CDDP
- ✓ Capecitabine-bevacizumab
- ✓ 5 FU-streptozotocin-bevacizumab
- ✓ Chemo-embolisation

Further information about the chemotherapy protocols above:

- ✓ FOLFIRI = Folinic acid + 5FU + irinotecan
- ✓ Simplified FOLFOX 4 (or modified FOLFOX 6) = Folinic acid + 5FU + oxaliplatin (Eloxatine®)
- ✓ XELOX = capecitabine (Xeloda)+ Oxaliplatin (Eloxatine®)

```
LV5FU2 = Leucovernin = Levamisol = folinic acid = 5FU
5FU = 5 Fluorouracil
```

- ✓ GEMOX = gemcitabine (Gemzar[®]) + oxaliplatin
- ✓ Irinotecan-CDDP = CCDP = Cisplatin
- ✓ Temozolomide-capecitabine (TEM-CAP) = Temodal®+Xeloda®
- ✓ Carboplatin-etoposide; etoposide=VP16
- ✓ Adriamycin-streptozotocin
- ✓ Adriamycin = doxorubicin
- ✓ Dacarbazine = Deticene[®] = DTIC
- ✓ Bevacizumab = Avastin[®]

10.2. Appendix 2: Alkyating Agents and Alkylating Treatment Protocols

Alkyating agents and alkylating treatment protocols are shown below:

- ✓ Dacarbazine
- ✓ Temozolomide
- ✓ Temozolomide-capecitabine (TEM-CAP)
- ✓ LV5FU2-dacarbazine
- ✓ Simplified FOLFOX 4 (or modified FOLFOX 6) = oxaliplatin (EloxatineR) + (EloxatineR) + simplified LV5FU2
- ✓ XELOX
- ✓ GEMOX = gemcitabine + oxaliplatin
- ✓ CDDP-etoposide
- ✓ Carboplatin-etoposide
- ✓ Irinotecan-CDDP
- ✓ Simplified FOLFOX 4 (or modified FOLFOX 6) = Folinic acid + 5FU + oxaliplatin (Eloxatine®)
- ✓ XELOX = capecitabine (Xeloda)+ Oxaliplatin (Eloxatine®)
- ✓ GEMOX = gemcitabine (Gemzar®) + oxaliplatin
- ✓ Irinotecan-CDDP (CCDP = Cisplatin)
- ✓ Temozolomide-capecitabine (TEM-CAP) = Temodal®+Xeloda®
- ✓ Carboplatin-etoposide; (etoposide=VP16)
- ✓ Dacarbazine = Deticene[®] = DTIC

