In localised forms, surgery is the gold standard curative treatment. In well-differentiated, localised, small tumours <2cm, treatment abstention may be justified with simple monitoring only, especially if the surgery proposed is a Whipple's procedure (pancreaticduodenectomy) and if the tumour is welldefined, rather than recourse to surgery which does remain the gold standard curative treatment.

In locally advanced or metastatic forms the following "anti-cancer" treatments are used (13-15):

- Hepatic (chemo)embolization, which is a good palliative option for patients who are not candidates for surgery (16)
- Chemotherapy: proven efficacy in well-differentiated pancreatic tumours (e.g. a combination of streptozotocin and 5-FU and/or doxorubicin with an objective response rate of around 35-40% (17-19))
- Somatostatin analogues
- Interferon alpha: 42% show symptomatic response (secretions) and 11% show tumour reduction
- Radionuclide therapy with radiolabelled somatostatin analogues

The following figure shows a treatment algorithm used in patients with pancreatic neuroendocrine tumours and based on the degree of differentiation (figure from publication (20)).

[figure not shown]

Figure 1 - Therapeutic algorithm for patients with well-differentiated and poorly differentiated pancreatic neuroendocrine tumours

Targeted therapies are systemic treatments that offer a new therapeutic option. There are two treatments that have shown efficacy in the therapeutic management of patients with unresectable pNET in placebo-controlled clinical trials (21, 22), particularly on a primary outcome measure of progression-free survival (PFS): sunitinib and everolimus. PFS was defined as the time between randomisation and the date of first documented disease progression or death, irrespective of the cause. The absolute gain in PFS was 5.9 months for sunitinib and 6.4 months for everolimus. The secondary outcome measures for both drugs were overall survival (defined as the time between randomisation and death irrespective of cause), the objective response percentage according to the RECIST criteria, the duration of response, safety and quality of life based on the EORTC QLQ-C30 scale (for sunitinib). Adverse effects were observed with a higher frequency in the everolimus and sunitinib groups than in the placebo groups.

On the basis of these trials, applications to extend the indications have been granted by the health authorities for both products.

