- Liver invasion at initiation of the ongoing treatment line or line started at inclusion $(\le 50\% / > 50\%)$.
- Number of metastatic sites when starting the current line of treatment or line of treatment started at inclusion (≤2 / >2). The "not reported" modality will be considered as missing data.

Chemotherapy

Chemotherapy will be described for each period (overall follow-up, before inclusion, after inclusion) and as follows:

- Number of patients having received chemotherapy at least once.
- Number of patients having never received chemotherapy.
- Number of chemotherapies received per patient (quantitative and by class: 0 / 1 / 2 / 3 / 4 and more).

• Number of patients having received chemotherapy and a somatostatin analog as main treatment.

In addition, the position of chemotherapy in the care pathway of the patient will be described for the entire follow-up:

- Number of patients having received chemotherapy as the 1st, 2nd, 3rd, nth main treatment line.
- Number of patients having received chemotherapy immediately before/after targeted therapy.
- Number of patients having received chemotherapy immediately before/after a somatostatin analog (as main treatment).
- Number of patients having received chemotherapy as 1st line at inclusion then targeted therapy as 2nd line (yes/no).
- Number of patients having received alkylating chemotherapy after inclusion (yes/no).
- Number of alkylating chemotherapies received after inclusion.

Alkylating agents are listed in Appendix 10.2.

Somatostatin analogs

Somatostatin analogs will be described for each period (entire follow-up, prior to inclusion, after inclusion) overall (main or combination treatment), if received as a main or combination treatment and as follows:

- Number of patients having received at least one somatostatin analog.
- Number of patients having never received a somatostatin analog.
- Number of somatostatin analogs received per patient (quantitative and by class: 0 / 1 / 2 / 3 / 4 and more).

In addition, the position of the somatostatin analog in the care pathway of patients will be described for the entire follow-up:

- Number of patients having received a somatostatin analog as the 1st, 2nd, 3rd, nth main treatment line.
- Number of patients having received a somatostatin analog in combination as the 1st, 2nd, 3rd, nth main treatment line.
- Number of patients having received a somatostatin analog as the 1st, 2nd, 3rd, nth main treatment line or in combination.

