9.3.2.1.2. Chemotherapy

Table 14.2.2.2.1: Number of Chemotherapy Patients – Reference Set – Analysis of the Period before Inclusion

		Total (N=XX)
Number of patients having received chemotherapy at least once before inclusion		XX (XX.X%)
Number of patients who never received chemotherapy before inclusion		XX (XX.X%)
Number of chemotherapies received per patient before inclusion	Missing data Mean (SD) Mean [Min; Max] [Q1; Q3]	XX XX XX.XX (X.XX) XX.X [XX.X; XX.X] [XX.X; XX.X]
	0 1 2 3 >3	XX (XX.X%) XX (XX.X%) XX (XX.X%) XX (XX.X%) XX (XX.X%)
Number of patients having received chemotherapy and a somatostatin analoganalog as main treatment before inclusion	ı	XX (XX.X%)

Using the same template:

Table 14.2.2.2.2: Number of Chemotherapy Patients – Reference Set – Analysis of the Period at Inclusion and after Inclusion

Table 14.2.2.2.2: Number of Chemotherapy Patients – Reference Set – Analysis of the Overall Follow-Up Period

Table 14.2.2.2.4: Position of Chemotherapy in the Care Pathway of Patients for the Entire Follow-Up – Reference Set –

		Total (N=XX)
Number of patients having received chemotherapy as the 1st main treatment line		XX (XX.X%)
Number of patients having received chemotherapy as the 2nd main treatment line		XX (XX.X%)
Number of patients having received chemotherapy as thenth main treatment line		XX (XX.X%)
Number of patients having received chemotherapy as the nth main treatment line		XX (XX.X%)
Number of patients having received chemotherapy immediately before targeted therapy		XX (XX.X%)
Number of patients having received chemotherapy immediately after targeted therapy		XX (XX.X%)
Number of patients having received chemotherapy immediately after a somatostatin analoganalog (as main treatment)		XX (XX.X%)
Number of patients having received chemotherapy immediately after a somatostatin analoganalog (as main treatment)		XX (XX.X%)
Number of patients having received chemotherapy as 1st line, then targeted therapy as 2nd line (at inclusion)		XX (XX.X%)
Number of patients having received alkylating chemotherapy at least once after inclusion		XX (XX.X%)
Number of alkylating chemotherapies received after inclusion	N	XX
	Missing data Mean (SD) Mean [Min; Max] [Q1; Q3]	XX XX.XX (X.XX) XX.X [XX.X; XX.X] [XX.X; XX.X]
	0 1 2 3 >3	XX (XX.X%) XX (XX.X%) XX (XX.X%) XX (XX.X%) XX (XX.X%)

Programmer note: add as a footnote the list of patients whose start date for their last main treatment line falls after the date of the last visit.

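### The SAP's list of alkylating chemotherapy omits all four streptozotocin regimens, so two descriptive rows will misclassify streptozotocin lines given after inclusion

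*SAP*

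**What the plan says.** The chemotherapy part of SAP 5.9.3 (Therapeutic Pathway of Patient) plans two outputs on alkylating treatment: a yes/no patient count and "Number of alkylating chemotherapies received after inclusion". For the definition it says only "Alkylating agents are listed in Appendix 10.2". The table of the position of chemotherapy in the care pathway (SAP 9.3.2.1.2) carries both outputs; its patient row reads "Number of patients having received alkylating chemotherapy at least once after inclusion". The SAP defines alkylating chemotherapy nowhere else.

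Appendix 2 opens with "Alkyating agents and alkylating treatment protocols are shown below" and lists dacarbazine, temozolomide and platinum regimens. Appendix 1, the list of main chemotherapy protocols, also names "LV5FU2-streptozotocin", "Adriamycin-streptozotocin", 5 FU-streptozotocin and 5 FU-streptozotocin-bevacizumab. None of these four is in Appendix 2.

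The protocol's Introduction (Therapeutic management) illustrates chemotherapy of proven efficacy in well-differentiated pancreatic tumours with "a combination of streptozotocin and 5-FU and/or doxorubicin with an objective response rate of around 35-40" per cent. The CRF has a tick box for streptozocin in the treatment at enrolment (CRF 2.3.1), in the previous lines (CRF 2.4) and in the new lines during follow-up (CRF 3.3, Table 5).

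**The concern.** Streptozotocin is a nitrosourea, which is a standard class of alkylating agent. That is general pharmacology and has to be brought in from outside, since neither document states the class of any of these drugs. A list headed as alkylating agents that leaves it out, yet admits oxaliplatin, cisplatin and carboplatin combinations, needs a reason, and the SAP gives none.

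Describing the types of treatment and regimens that patients receive is a secondary objective (protocol 3.2, SAP 3.1.2). A programmer following Appendix 2 will code streptozotocin lines as not alkylating. The resulting rows will carry a label that a clinical reader takes to include the very combination the protocol uses as its example.

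**Working it through.** The plan states no figure for these rows (the templates show XX), so there is nothing to reproduce. The check is a comparison of the two lists, followed by tracing what the rule does to each kind of patient.

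**Step 1: compare the lists.**

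| | Count | Content |
|---|---|---|
| Appendix 1 entries | 19 | all main protocols |
| of which with streptozotocin | 4 | LV5FU2-, 5 FU-, Adriamycin-, and 5 FU- with bevacizumab |
| Appendix 2 distinct regimens | 10 | 4 dacarbazine or temozolomide + 6 platinum |
| of which with streptozotocin | 0 | none |

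The four are dacarbazine, temozolomide, temozolomide-capecitabine and LV5FU2-dacarbazine. The six are FOLFOX, XELOX, GEMOX, CDDP-etoposide, carboplatin-etoposide and irinotecan-CDDP.

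All 10 Appendix 2 regimens appear in Appendix 1 in the same order, so Appendix 2 reads as a filtered copy. The entries not carried over number 19 − 10 = 9: the four streptozotocin regimens plus interferon alpha-2, FOLFIRI, simplified LV5FU2, capecitabine-bevacizumab and chemo-embolisation. The missing streptozotocin entries stood in different places in Appendix 1, and the Adriamycin-streptozotocin note is gone from the explanatory lines as well, while neighbouring entries survive. Damage in text extraction is therefore unlikely.

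**Step 2: test whether a consistent definition gives this list.**

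- Strict (classical alkylators, no platinum): 4 dacarbazine/temozolomide + 4 streptozotocin = 8 regimens. Appendix 2 lacks 4 of these and has 6 extra.
- Broad (classical alkylators plus platinum): 10 + 4 = 14 regimens. Appendix 2 lacks 4 and has none extra.
- As written: 10 regimens, obtained only by keeping platinum and dropping streptozotocin.

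Under either definition the four streptozotocin regimens belong on the list.

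**Step 3: apply the rule to patients.**

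| Chemotherapy after inclusion | Patient row | Count of alkylating chemotherapies |
|---|---|---|
| Streptozotocin, no listed regimen | 'no', should be 'yes' | short by each streptozotocin line |
| Streptozotocin and a listed regimen | 'yes', correct | short by each streptozotocin line |
| Streptozotocin only before inclusion | outside the row | outside the row |
| Platinum regimen only | 'yes', correct only if platinum is meant to count | counted, on the same condition |

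**Step 4: size.** Patients missed = N × s, where N is the number on chemotherapy after inclusion and s is the share of them whose only alkylating regimen contains streptozotocin. Neither value is in the documents. As pure assumption, with N from 40 to 75: s = 0 gives 0 patients, 40 × 0.10 gives 4, and 75 × 0.40 gives 30. This shows scale only and is not an estimate.

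**The case against.** The strongest reply is that this matters little. The two rows belong to the additional analyses of SAP 5.9. The management analysis in SAP 5.6.1 does not mention alkylating agents. No PFS or OS subgroup in SAP 5.9.7 and 5.9.8 uses the flag, and no safety analysis does. Streptozotocin use also remains visible elsewhere: treatment at inclusion is described by the Appendix 1 protocols (SAP 5.4.1), and lines during follow-up are listed patient by patient. All of this stands, and it limits the point to two rows.

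A reader might infer more than the documents support:

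- *That every streptozotocin patient is counted as not having received alkylating chemotherapy.* The patient row asks for at least one alkylating chemotherapy after inclusion, so anyone who also received a listed regimen in that period is still counted.
- *That both counts are simply too low.* If platinum is not meant to count, the six platinum regimens push the counts up and the net error could go either way. If no streptozotocin line falls after inclusion, there is no undercount.
- *That 4 missing out of 14 names, or 29%, measures the error.* This counts entries on a list, not patients, and it counts platinum as alkylating.
- *That streptozotocin use must be common.* The Introduction gives it as an example in background text, and a tick box shows that it can be recorded, not how often it is.

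The omission might also be a deliberate grouping that nobody explained; the documents do not say. That possibility does not rescue the list as it stands, because the rows are labelled as alkylating without qualification.

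**Conclusion.** The point holds within narrow limits. Appendix 2 is the sole definition behind the two rows, and it leaves out all four streptozotocin regimens that Appendix 1 names. Followed exactly, it excludes every streptozotocin line received after inclusion from the count of alkylating chemotherapies and records 'no' for each patient with no other alkylating regimen in that period.

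This rests on one fact from outside the documents, the drug class of streptozotocin. The size cannot be determined without usage data, and the net direction cannot be determined until the SAP says whether platinum counts. The consequence is a misleading description of management in two rows; the estimates for the primary objective do not change.

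**What to change.** Add LV5FU2-streptozotocin, 5 FU-streptozotocin, Adriamycin-streptozotocin and 5 FU-streptozotocin-bevacizumab to Appendix 2.

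Derive the flag from agents and not from regimen names: alkylating is 'yes' if streptozocin, dacarbazine or temozolomide is recorded, alone or in combination, including entries typed as free text under 'Other'. This also catches combinations that neither appendix names.

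State whether platinum agents count. If they do, label both rows 'alkylating or platinum' and search the free text for them too, since carboplatin has no CRF tick box. If streptozotocin was left out on purpose, give the reason and relabel the rows accordingly.

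The cost is one appendix edit, one change to the code list and a read through the free-text chemotherapy entries before the table is programmed. No new data are needed.
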